3.3. Study Endpoints

3.3.1. Primary Efficacy Endpoint

The primary efficacy endpoint is the occurrence of any SSI within 30 days after surgery

3.3.2. Safety Endpoints

Safety endpoints will be analyzed over the entire treatment and follow-up period.

- AEs (including specifically local application site reactions and allergic reactions)

4. DEFINITION OF ANALYSIS SETS

The study analysis populations will consist of the following:

Full Analysis Set [modified intention-to-treat (mITT) analysis set]: The mITT analysis set includes all patients who were randomized to study treatment, received the study treatment, and underwent surgery. Subjects will be analyzed by treatment received, not treatment randomized.

Safety Analysis Set: This is all patients that received study treatment. Patients are assigned to the treatment given, not randomized. If this set is different from mITT then it will be used in analysis and listings for adverse events

Per Protocol Analysis Set: The per-protocol (PP) subset includes all full analysis set patients who had final follow-up at 30 days post-surgery.

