Main Inclusion/Exclusion Criteria: Patients will be males and females at least 18 years of age scheduled to undergo clean (class I wound) or clean-contaminated (class II wounds) surgeries (see Appendix A for examples).	

Investigational Product, Dosage and Mode of Administration:

██████████ 26-mL Applicator will be applied topically to the region of surgical incision using repeated back and forth strokes. For dry surgical sites such as the abdomen or arm, the product will be applied for a period of at least 30 seconds and for moist surgical sites (such as the inguinal fold) for 2 minutes. The application area should be allowed to air dry for approximately 3 minutes.

Reference Therapy, Dosage and Mode of Administration: █████ will be applied according to the prescribing information.

Duration of Study: Each patient will participate in the study for up to 51 days, including up to 21 days for screening and 30-days of post-surgical follow-up for evidence of any SSI or other AEs.

Criteria for Evaluation:

Primary Efficacy Endpoint: The primary efficacy endpoint is the occurrence of any SSI within 30 days after surgery. A secondary analysis of the primary efficacy endpoint are subgroup analyses including:

- Different types of SSI classified as superficial incisional infection, deep incisional infection, or organ-space infection
- Clean (class I wound) or clean-contaminated (class II wounds) surgeries

Safety Endpoints: Safety endpoints will be analyzed over the entire treatment and follow-up period.

- AEs (including local application site reactions and allergic reactions)

Statistical Methods:

Analysis Populations: The full analysis set includes all patients who were randomized to study treatment, received the study treatment, and underwent surgery. The per-protocol (PP) subset includes all full analysis set patients who had final follow-up at 30 days post-surgery. The safety subset will include all patients who were randomized to the study and received a study treatment and will be analyzed as they were treated.

Statistical Analyses: All baseline data and efficacy and safety endpoints will be presented by descriptive statistics including numbers and percentages for categorical variables and mean, standard deviation (SD), median, minimum and maximum values for continuous variables. All data will be presented for all three of the analysis sets.

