7.4. Measures Taken to Minimize/Avoid Bias

7.4.1. Randomization (Day 1)

If eligible for the study, patients will be randomized in an approximate 1:1 ratio to have the skin at the surgical site scrubbed with the [REDACTED] or [REDACTED] applicator. A

stratified permuted block randomization procedure will be performed via an interactive web-based randomization system (IWRS) with type of surgery [clean (class I wound) or clean-contaminated (class II wounds) surgery]) as the stratification variable.

If the patient is randomized and is never treated with one of the investigational products or never underwent surgery, then the patient will be considered a randomization failure and an additional patient will be randomized with the next randomization sequence at the time he/she is randomized. The reason(s) that a patient was considered a randomization failure or screen failure will be documented in source documents and eCRFs.

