11.2. Analysis Sets

The full analysis set includes all patients who were randomized to study treatment, received the study treatment, and underwent surgery. The per-protocol (PP) subset includes all full analysis set patients who had final follow-up at 30 days post-surgery. The safety subset will include all patients who were randomized to the study and received a study treatment and will be analyzed as they were treated. All analyses will be performed for each analysis set.

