5. HYPOTHESES TO BE TESTED

This is a descriptive study. No hypothesis testing will be performed.

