8.4. Efficacy Analysis

8.4.1. SSI Rates

The number and percentage of patients who were diagnosed with an SSI at any time post surgery will be presented to the full analysis set and the PP analysis set. The rates by type of SSI, superficial incisional, deep incisional, and organ space will also be summarized. A listing will be provided by patient that includes these endpoints as well as the medical findings that contributed to each diagnosis.

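### The SAP groups its modified intention-to-treat set by treatment received, so no visible SSI table compares the arms as randomised

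*SAP*

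**What the plan says.** SAP section 4 equates the full analysis set with an mITT set: patients who were randomised, treated and operated on. Its grouping rule is "Subjects will be analyzed by treatment received, not treatment randomized". The safety set has the same as-treated rule. The per-protocol (PP) set is the part of the full set with Day 30 follow-up. It has no grouping rule of its own and does not require that the assigned product was the one used.

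SAP 8.4.1 says that SSI counts and percentages "will be presented to the full analysis set and the PP analysis set". The list of shells in SAP section 10 matches: Table 8 (SSI, mITT), Table 9 (SSI, PP), and Tables 10 and 11 (patients with an SSI). The only visible table on all randomised patients is Table 1, disposition.

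Protocol 11.2 defines the same full set but does not say how it is grouped. It states an as-treated rule only for the safety subset, whose patients "received a study treatment and will be analyzed as they were treated". It adds "All analyses will be performed for each analysis set", and the Synopsis has "All data will be presented for all three of the analysis sets". SAP section 5 states "This is a descriptive study. No hypothesis testing will be performed".

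**The concern.** An intention-to-treat label, modified or not, tells the reader that patients are counted in the arm they were allocated to. Here the next sentence rules that out. The SAP does not contradict the protocol, which is silent on grouping for the full and PP sets. It fills the gap by extending the safety rule to efficacy, and gives no visible reason.

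The trial is randomised 1:1 by stratified permuted blocks, which the protocol presents as a measure against bias (Protocol 7.4.1). Its main output is two SSI rates that will be read side by side. Regrouping a patient by the product received gives up the protection of randomisation for that patient. If the reason for the switch is linked to infection risk, the difference between the two rates is biased.

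**Working it through.** **Plan's own figures.** There is none to reproduce on this point. The only design number is the sample size, 100 + 100 = 200, which SAP section 6 calls a convenience sample. No alpha, power, margin or crossover rate is given.

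**Step 1: trace each visible SSI table to its grouping rule.**

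| Table | Set | Grouping | Basis |
|---|---|---|---|
| 8 | mITT | As treated | Explicit, SAP section 4 |
| 9 | PP | As treated | Inferred: subset of mITT, no rule of its own |
| 10, 11 | Patients with an SSI | As treated | Inferred: section 4 defines no such set |

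The protocol's statement that every analysis is run on every set adds only the safety set, which is also as treated. None of the four visible SSI tables is therefore by randomised arm. Only table titles are visible; the shells and listings are not, and they are not judged.

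**Step 2: size of the effect (illustration).**

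Inputs from the documents: 100 per arm (SAP section 6); infection risk of at most 2% for clean surgery and 5 to 15% for clean-contaminated surgery (Protocol Appendix A).

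Assumptions: the two products are equally effective; clean risk is 2%; clean-contaminated risk p is 5% or 15%; the mix of clean to clean-contaminated is 50/50 or 80/20; only clean-contaminated patients switch, all from A to B.

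With c clean and k clean-contaminated patients per arm (c + k = 100) and x switches:

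- rate A = (0.02c + p(k − x)) / (100 − x)
- rate B = (0.02c + p(k + x)) / (100 + x)
- P = (0.02c + pk) / 100, and SE of the difference = √(2P(1 − P)/100)

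Worked case, 50/50, p = 15%, x = 5: A = (1 + 6.75)/95 = 8.16%; B = (1 + 8.25)/105 = 8.81%; gap 0.65 points. P = 8.5%, so SE = 3.94 points.

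| Mix, p | SE (points) | x = 1 | x = 2 | x = 5 | x = 10 |
|---|---|---|---|---|---|
| 50/50, 5% | 2.60 | 0.03 | 0.06 | 0.15 | 0.30 |
| 50/50, 15% | 3.94 | 0.13 | 0.26 | 0.65 | 1.31 |
| 80/20, 5% | 2.25 | 0.05 | 0.10 | 0.24 | 0.48 |
| 80/20, 15% | 2.96 | 0.21 | 0.42 | 1.04 | 2.10 |

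Entries under x are the spurious gap in percentage points; the true difference is 0. As a fraction of one SE, the range is 0.03/2.60 = 0.01 to 0.42/2.96 = 0.14 for 1 or 2 switches, and 0.15/2.60 = 0.06 to 2.10/2.96 = 0.71 for 5 or 10. The larger counts are extreme: they need 10 to 20% (50/50) or 25 to 50% (80/20) of one arm's clean-contaminated patients to switch in one direction. With no switches, or equal switches both ways within the stratum, the gap is 0.

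Wound class stands in here for any risk factor linked to switching. Rates by wound class (Protocol 8.1.1) would remove the gap in this illustration, but not one driven by risk within a class.

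**Step 3: observed counts.** The figures above are expected values, and few events are likely. Suppose both randomised arms have the same number of SSIs, and one patient given the wrong product is among them. With 2 SSIs per arm, the as-treated rates are 1/99 = 1.01% and 3/101 = 2.97%, a shift of 1.96 points. With 15 per arm they are 14/99 = 14.14% and 16/101 = 15.84%, a shift of 1.70 points. This is reclassification rather than expected bias, but it shows why both groupings should be visible.

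**The case against.** The case for leaving the rule alone has substance. The study is descriptive, and no difference, ratio or confidence interval is visibly planned. The objective concerns two products, so a rate per product applied can be defended.

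Opportunity for risk-linked switching looks limited. Treatment is one application lasting minutes (Protocol 7.10), component allergies are excluded (7.3.2), and eligibility is rechecked before randomisation on the day of surgery (10.3).

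As-randomised grouping has its own cost. If the true difference were 5 points and 2 of 100 patients in one arm switched at random, it would show 5 × 0.98 = 4.9 points. That 0.10-point dilution is of the same order as the bias computed for 1 or 2 switches.

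An as-randomised count might also be recovered from the by-patient SSI listing (SAP 8.4.1) and the randomisation schedules in the final report (Protocol 15). Finally, a PP set grouped as randomised would still hold patients given the wrong product.

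What stands is that the expected effect is small and the documents show no mechanism for bias. What does not stand is the conclusion that nothing need change. Removing the test does not remove the comparison that randomisation was set up to support. A count the reader could reconstruct is not a planned analysis, and deviation summaries by type (SAP 8.2) do not give an SSI rate. The dilution argument supports showing both groupings. The PP weakness comes from that set's existing definition and does not touch the main correction.

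**Conclusion.** The concern holds. The as-treated rule is explicit for the mITT set and Table 8, and inferred for Tables 9 to 11. No visible SSI table is by randomised arm. No test or decision rule is affected, and the effect is nil without crossovers or if errors are unrelated to risk.

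Under the assumptions above, the bias is at most 0.42 points (0.14 SE) for 1 or 2 one-way switches. It reaches 2.10 points (0.71 SE) only in an extreme case. It is unlikely to dominate the result, but it can be avoided cheaply and should be fixed before database lock. Renaming the set would correct the label without supplying the missing rate.

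**What to change.** Before database lock:

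1. In SAP section 4, replace the as-treated sentence with: patients in the full analysis (mITT) set are analysed in the arm to which they were randomised. Apply this to the mITT tables other than adverse events (2, 4, 6, 8, 12). State that the PP tables (3, 5, 7, 9, 13) and Tables 10 and 11 use the same grouping.
2. Add one sensitivity table of SSI rates in the full set by treatment received, because as-randomised rates mix products if crossovers occur.
3. Run all adverse-event tables (14 to 20) on the safety set by treatment received, and delete the condition "If this set is different from mITT then it will be used in analysis and listings for adverse events". After step 1 the two sets could hold the same patients but group them differently, so the condition would no longer work.

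Two reporting additions would help but are secondary. Give the number of patients whose treatment differed from assignment, in Table 1 if it is not already there. Also say plainly that the mITT set is not a full intention-to-treat set: if a patient is randomised but never treated or never operated on, "then the patient will be considered a randomization failure and an additional patient will be randomized with the next randomization sequence" (Protocol 7.4.1).

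The cost is a few sentences, one extra SSI table and retitled adverse-event shells, with no new data. If there are no crossovers, the two SSI tables will be identical.

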5. HYPOTHESES TO BE TESTED

This is a descriptive study. No hypothesis testing will be performed.

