Appendix A. Wound Classifications

Classification	Examples of Procedures
Class I: Clean Risk of infection: $\leq 2\%$	
• Hernia repair• Mastectomy• Total hip or knee replacement• Vascular/cardiovascular procedures
Class 2: Clean/Contaminated Risk of infection: 5-15%	
• Cholecystectomy (chronic inflammation)• Colectomy

From: [REDACTED]

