3 PROTOCOL SUMMARY

3.1. Study Objectives

3.1.1. Primary Efficacy

The primary efficacy objective of this study is to determine the efficacy of two skin preparation products, [REDACTED] and a standard of care product, [REDACTED] on the rates of surgical site infections (SSI).

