3.2. Study Design

This study is a 2-arm, randomized, parallel group, single-site study designed to determine the SSI rates within 30-days post-surgery of pre-surgical skin cleansing with [REDACTED] and [REDACTED] on patients who are planning to undergo clean (class I wound) or clean-contaminated (class II wounds) surgery based on medical chart review. After consenting to the study, screening will be conducted to determine patient eligibility. Eligibility will be determined from chart review and conducting any procedures for information not in the medical chart (e.g., signs of infection at the surgical site where an incision will be performed or patient reported allergies to components of the surgical scrubs). Pre-operative data to be collected on electronic case report forms (eCRFs) include patient's demographics, medical history, current antibiotics (last 4 days), adherence to [REDACTED] standard preop surgical instructions, and record of planned surgery. Eligible

patients will be randomized with stratification by type of surgery (clean versus clean-contaminated) in a 1:1 ratio to receive skin pretreatment with either [REDACTED] or [REDACTED] and will undergo surgery. The surgical site will be examined for signs of infection and local skin reactions at least once a day during hospitalization, and at discharge. The patient will be contacted by telephone approximately 3-to-5 days post hospital release and at 30-days post the day of surgery. During these telephone contacts, the patient will be asked about signs of local skin or systemic allergic reactions and a general question about how they are feeling to determine if any other AEs may have occurred. If during these queries, the patient reveals any events that may be indicative of an SSI, they will be asked to see a study doctor to determine if an SSI has occurred. If they have visited another doctor for an evaluation, the patient will be asked to provide any relevant medical records to include in the study files. At any time after discharge up to 30 days post-surgery, the patient will be encouraged to call a study nurse or doctor and arrange for a prompt clinical evaluation if an infection is suspected.

Study assessments and procedures will be performed at the visits and time points outlined in the Schedule of Assessments (**Table 1**).

Table 1: Schedule of Assessments

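### The primary SSI rates are to be reported as counts and percentages only, with no confidence interval and no between-arm estimate, in a randomized controlled trial with an efficacy objective

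*SAP*

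**What the plan says.** - **Objective.** SAP 3.1.1: "The primary efficacy objective of this study is to determine the efficacy of two skin preparation products", measured on SSI rates. Protocol section 4 has the same objective. Neither states a direction, margin or target difference.
- **Design.** SAP 3.2 describes a trial "designed to determine the SSI rates within 30-days post-surgery of pre-surgical skin cleansing" with each product, in which "patients will be randomized with stratification by type of surgery (clean versus clean-contaminated) in a 1:1 ratio". Protocol 7.4.1 adds that a "stratified permuted block randomization procedure will be performed via an interactive web-based randomization system (IWRS") with wound class as the stratification variable. The reference is the standard-of-care chlorhexidine and alcohol applicator.
- **Endpoint.** SAP 3.3.1: "The primary efficacy endpoint is the occurrence of any SSI within 30 days after surgery".
- **Inference.** SAP 5: "This is a descriptive study. No hypothesis testing will be performed". SAP 6 calls the 200 patients (100 per arm) a convenience sample.
- **Analysis.** SAP 8.4.1: "The number and percentage of patients who were diagnosed with an SSI at any time post surgery will be presented" for the full and per-protocol sets. Protocol 11.3 has the same sentence. The general rules (SAP 8.1, protocol 11.1) likewise give only numbers and percentages for dichotomous variables.
- **Completeness.** SAP 2 says that the SAP holds all planned analyses.
- **Wound class.** Protocol 8.1.1 lists SSI rates by clean and clean-contaminated surgery as a secondary analysis. SAP 8.4.1 and the titles of the SSI tables do not mention it. SAP 8.3 has wound class only as a baseline characteristic.

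**The concern.** Both arms receive an active antiseptic and there is no untreated group. An arm's percentage depends heavily on the mix of surgery, since Appendix A gives an infection risk of at most 2% for clean surgery and "Class 2: Clean/Contaminated Risk of infection: 5-15%" for the other class. The randomized contrast with the reference product is what speaks most directly to efficacy, and no available text specifies it.

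What is at stake is how the result can be read. Two percentages under an efficacy objective, with no interval, leave open whether a small gap or near-equality means anything. Choosing not to test does not remove the need to show precision, least of all when the sample size has no precision rationale of its own.

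**Working it through.** **The plan's own figure.** The planned size is 2 x 100 = 200. There is no alpha, power, effect size, margin or target interval width, so nothing further can be reproduced.

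**Inputs.** n = 100 per arm (SAP 6). Plausible rates come from Appendix A: up to 2% for class I and 5% to 15% for class II. The class mix is not stated. With a share s of class II, and class I taken at 2%, the overall rate lies between (1 - s) x 2% + s x 5% and (1 - s) x 2% + s x 15%. At s = 0.5 that is 3.5% to 8.5%. The event counts below are assumptions chosen to span 2% to 15%.

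**Formulas (95%, z = 1.96).**
- Exact (Clopper-Pearson) interval for x/n: lower limit = 2.5% quantile of Beta(x, n - x + 1); upper limit = 97.5% quantile of Beta(x + 1, n - x).
- Wilson limits (l, u) for p = x/n: [p + z²/(2n) ± z√(p(1 - p)/n + z²/(4n²))] / (1 + z²/n).
- Newcombe interval for d = p1 - p2: lower = d - √((p1 - l1)² + (u2 - p2)²); upper = d + √((u1 - p1)² + (p2 - l2)²).

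**5 v 5 in full.** Wilson limits for 5/100 are 0.0215 and 0.1118. The half-width is √((0.05 - 0.0215)² + (0.1118 - 0.05)²) = √(0.00081 + 0.00381) = 0.068, which is 6.8 points.

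**3 v 6 in full.** Wilson limits are 0.0103 to 0.0845 for 3/100 and 0.0278 to 0.1248 for 6/100.
- Lower: -0.03 - √((0.03 - 0.0103)² + (0.1248 - 0.06)²) = -0.098.
- Upper: -0.03 + √((0.0845 - 0.03)² + (0.06 - 0.0278)²) = +0.033.

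| Assumed SSIs per 100 | Exact 95% CI, each arm | Difference, points | Newcombe 95% CI, points |
|---|---|---|---|
| 2 v 2 | 0.2% to 7.0% | 0 | -5.2 to +5.2 |
| 5 v 5 | 1.6% to 11.3% | 0 | -6.8 to +6.8 |
| 3 v 6 | 0.6% to 8.5%; 2.2% to 12.6% | -3.0 | -9.8 to +3.3 |
| 10 v 10 | 4.9% to 17.6% | 0 | -8.7 to +8.7 |
| 15 v 15 | 8.6% to 23.5% | 0 | -10.1 to +10.1 |

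At 2% and 5% the half-width exceeds the rate itself (5.2 v 2; 6.8 v 5). At 10% and 15% it does not (8.7 v 10; 10.1 v 15), though it is still more than half the rate. These intervals are unstratified and assume complete follow-up.

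**What an interval would not repair.** Assuming a two-sided 5% test and a true halving of the rate, power at 100 per arm is 8% (2% to 1%), 15% (5% to 2.5%), 27% (10% to 5%) and 39% (15% to 7.5%).

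**The case against.** The strongest defence is that the plan is consistent on its own terms. The objective is not worded as a comparison, the design text speaks of determining rates, and the SAP openly declares a descriptive study on a convenience sample. A count and percentage is a point estimate of each rate. No passage plans a superiority, non-inferiority or equivalence claim for SSI, so a misreading of the result is a risk and not something the plan intends.

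This stands against stronger conclusions that a reader might draw:
- *That the objective cannot be answered.* Each rate is estimated, and a reader could form a crude difference. What is missing is the precision and a pre-specified contrast.
- *That randomization and stratification go unused.* Stratified allocation balances wound class between arms whatever the analysis, and protocol 8.1.1 plans rates by wound class. The narrower fault is that the SAP's SSI analysis does not carry that breakdown forward.
- *That the no-testing sentence is the error.* It excludes tests only. The gap lies in SAP 8.4.1 and 8.1.
- *That the plausible difference always exceeds the rates.* This holds at 2% and 5%, but not at 10% or 15%.

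Two limits of the evidence also stand. Only the titles of Tables 8 and 9 are available, so an interval inside those shells cannot be excluded. Display by arm is inferred, because SAP 8.4.1 does not name treatment group.

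The defence does not explain why a study meant to determine rates should show no precision for them.

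**Conclusion.** The point holds as a gap in estimation and reporting. The primary endpoint of a 1:1 stratified randomized trial has no specified interval for either arm and no specified between-arm estimate. At 100 per arm with equal observed rates, the omitted interval for the difference would run from about ±5 points (2% v 2%) to ±10 points (15% v 15%), so similar percentages would not show similar efficacy. The size rests on assumed event counts guided by Appendix A, an unstated wound-class mix, and unstratified intervals with no dropout. Adding intervals would make the limits of 200 patients visible; it would not make that number adequate for a comparative conclusion.

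**What to change.** 1. Keep the no-testing statement in SAP 5. Reword the objective in both documents as estimating the 30-day SSI rate in each arm and the difference between arms.
2. In SAP 8.4.1 and Tables 8 and 9, name treatment group as the display variable and add an exact 95% confidence interval for each arm's rate.
3. Add the risk difference (test minus reference) with a 95% interval by a method suited to small counts (Miettinen-Nurminen or Newcombe), stratified by randomized wound class, without a p-value.
4. Compute that difference by randomized arm. SAP 4 analyses the full set by treatment received, so any patient given the other product would turn the estimate into an as-treated contrast.
5. Carry the protocol's SSI rates by wound class into SAP 8.4.1 and the tables.
6. State that 200 patients support no claim of superiority, non-inferiority or equivalence.

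The cost is an edit to the objective, SAP wording and a few lines of SAS, with no extra patients or data. The downside for the sponsor is that the wide interval will be on view.
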